### **Recruitment Method:**

We plan to include pediatric patients who are scheduled for inpatient surgery at BCH over a period of 2 years. Patients will be recruited by members of the study staff. We will contact all patients and/or families scheduled for an eligible ERAS procedure (see below for details of contact methods) and otherwise meet criteria.

Each morning, a designated member of the study staff will review the upcoming surgical schedule to identify pediatric cases that fit the study criteria (procedure type and age). If these criteria are met, the case will be sent to an investigator for further clinical review. A final eligibility decision will be made by the PI.

1. ***Outpatients with procedures scheduled >2 weeks from identification:*** Patients will be sent information on the study (cover letter, brochure, consent form) up to 2 weeks prior to their surgery or scheduled preoperative visit. This will be sent either by USPS mail or by secure electronic mail if an e-mail is on file.
2. ***Outpatients with procedures scheduled 2 weeks or less from identification:*** Patients will be contacted by secure electronic email and/or given informational materials at their preoperative visit if we are unable to send mailers reliably VIA USPS. We will allow at least a day for them to consider participating in the study.
3. ***Outpatient telephone follow-up:*** Patients sent information packets either by USPS or secure electronic email may be contacted by telephone to confirm receipt of the materials and answer any initial questions after such time as they would normally be expected to have received and reviewed the packets (the next week for USPS and no sooner than 1 day following email). If materials have not been received, patients will be given the opportunity to have those materials sent or be contacted at a preoperative visit.
4. ***Inpatients with no planned discharge and/or preoperative clinic appointments:*** Patients who are already inpatient will be approached on the

patient floor or other inpatient encounter with study information. We will approach as soon as we have confirmed eligibility and will provide them with recruitment materials prior to their day of surgery and allow at least 24 hours for a decision to be made.

5. ***International patients:*** For international patients meeting entry criteria, recruitment materials will not be mailed internationally. If an e-mail is available for an eligible international patient, a secure e-mail via BCH server will be sent to the family. The e-mail will include all approved recruitment documents. If we are unable to reach an international family via e-mail, eligible international patients and their families will be approached and provided materials in the preoperative clinic. At this time we will provide information about the study, answer all questions and allow at least 24 hours for them to consider participating in the study.

6. When feasible, consent will be obtained either at the time of the preoperative visit, on the day of surgery, or at the bedside for those who are inpatient (i.e. without pre-op appointments). When in person consent is not feasible, the research team will have the consent discussion by phone prior to the day of surgery and families will be asked to provide written consent following that discussion. Written consent may be done through the RCS e-consenting platform or by sending the consent to the home by mail or email and receiving a signed copy of the consent back by mail or email.

7. In the exceptional situation when bilateral erector spinae blocks are used clinically and the patient or family were not approached for the study because of changes in the surgical schedule or other special situation, the research team can approach the families to offer participation in the study if they meet entry criteria.

We have numerous recruitment strategies as cardiac surgical scheduling is very fluid, often with cases added only days before. Our recruitment scheme allows for physical and electronic mail, on-site (clinic, inpatient) encounters, and phone calls to assess interest. We allow ourselves a maximum of 3 patient contacts. Consent may be taken at any time a patient feels comfortable to do so, but never with less than a day for patients/families to think or (re)consider. While we do allow ourselves to take consent on the day of surgery, we would not endeavor to meet the patient, describe the study, and take consent all at once on immediately prior to being taken into the OR for the procedure and would ensure that this would be done a minimum of 24h prior.

It will be made clear to all eligible participants that while BESBs are used in other types of patient groups, they are not typically used for patients undergoing congenital cardiac surgery via a sternotomy at BCH, and are therefore considered to be under investigation in this study. Families will be informed that the study is being done to better understand if using ESBs bilaterally is an effective form of pain management for patients undergoing sternotomy when compared to a set of matched historical patients who did not receive BESBs, and whose pain management includes a multimodal pain strategy, cornerstone of the ERAS Cardiac program. Research staff will stress that if families elect not to participate, they will not receive the BESBs unless agreed upon with their primary anesthesia team, but instead the standard of care pain management at BCH (multimodal pain regimen including pain-score based systemic opioid therapy as part of the ERAS Cardiac program guideline and orderset).

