### **(3) Description of Study Treatments or Exposures/Predictors**

Participants will have their medical record reviewed following enrollment for demographic information including: gender, age, weight and height, procedure, surgeon, and current and historical medication use.

Any other routine standard-of-care data will be collected preoperatively as well in addition to research-specific data points.

All enrolled patients will have bilateral erector spinae blocks (with catheters for postoperative local anesthetic infusion) placed by the by a member of the BCH regional anesthesia team (under the supervision of a member of the research team) in a sterile fashion after the cardiac surgical procedure is completed. The placement is as follows:

- The patient is placed in a lateral decubitus position (left or right), with all pressure points padded in routine fashion.
- The area for intervention is prepped with a chlorhexidine solution, and sterile drapes are applied to demarcate the block placement area.
- The T4/5 transverse process on one side is identified with the ultrasound transducer in a parasagittal orientation.
- An 18g Tuohy needle is advanced to the target area under direct ultrasound visualization. The needle tip is advanced until it contacts the transverse process, just below the erector spinae muscle complex.
- Normal saline is injected to confirm appropriate needle tip position. The erector spinae muscle is visualized to be elevated up off of the transverse process with normal saline injection
- With confirmation of appropriate needle tip position, the initial local anesthetic bolus is injected using a standard, weight-based dosing protocol.

- Following the bolus injection, a catheter is threaded into the space occupied by the local anesthetic bolus.
- Catheter tip position is verified by one or more of the following: ultrasound visualization of the catheter tip, ultrasound visualization of instilled normal saline and/or ultrasound visualization of a small hyperechoic (i.e. bright on ultrasound) injection of air.
- With the catheter tip position identified, the catheter is tunneled to a cutaneous exit point approximately 2-3cm from the incision using a Crawford needle.
- The catheter is dressed in standard fashion with an adhesive catheter anchor, Dermabond, Mastisol, Tegaderm and tape.
- This is repeated for the contralateral side. To the extent possible, this will be done without repositioning in a contralateral decubitus position.

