In addition to observational tools and subjective scoring, patient functional status (activity, sleep quality and other measures) will be assessed by actigraphic analysis using the Fitbit™ Charge 3 smartwatch. A Fitbit™ will be placed on the non-dominant arm, if possible, after extubation on the day of surgery. The Fitbit™ will remain on the patient until discharge from the hospital (which on average is about 5 days post-op) and the actigraphic data subsequently will be downloaded to the secure research database and the data wiped from the device. If a study subject had an unforeseeable complication and they no longer progressed along the standard recovery path (e.g. re-intubation, return to ICU), or if the watch was interfering in clinical care in any way, the Fitbit™ would be removed.

Following primary data collection for the enrolled subjects, each subject will be matched by surgical procedure using the STS procedure code, to 2 patients within the cardiac surgery ERAS program QI database (IRB #P00029161 which allows retrospective data analysis of outcomes) by the research team. All patients recruited for this study are themselves already part of the enhanced recovery after cardiac surgery clinical program [QIP]. Matching will be performed 1:2 with respect to surgical procedure and diagnosis using the STS codes, within 30% of the study patient's age and according to gender (if possible) and will be blinded to outcomes. Thus, up to 90 additional patients will be included in this study, retrospectively in addition to the 45 study patients from the single arm interventional cohort study (BESB).

Groups will be compared for demographic data, risk factors (from the STS database), diagnosis, procedure and cardiopulmonary bypass and clamp times to ensure their similarities

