## **E. Definition of Primary and Secondary Outcomes/Endpoints**

### **Primary:**

- Analgesic requirements, rendered as opiate equivalents, at 12, 24 and 48 hours, and the 24 hours preceding both 72 and 96 hours postoperatively.

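### Recruitment item 7 leaves open enrolment after a clinical BESB, when early outcomes can be known, with no logging, flagging or separate analysis of such patients

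*Combined protocol and SAP*

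**What the plan says.** Item 7 of the Recruitment Method (Section D(2)) is reserved for cases it calls exceptional. Its main trigger is that "bilateral erector spinae blocks are used clinically and the patient or family were not approached for the study because of changes in the surgical schedule". A second trigger, added to the first, reads "or other special situation" and is not defined. For patients who meet either trigger, "the research team can approach the families to offer participation in the study if they meet entry criteria". The item gives no time limit and no cap.

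Other parts of the protocol bear on the timing:

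- Blocks are placed "in a sterile fashion after the cardiac surgical procedure is completed" (Section D(3)).
- Consent is taken "never with less than a day for patients/families to think or (re)consider" (Recruitment Method, closing paragraph). For day-of-surgery consent, the same paragraph says the team "would ensure that this would be done a minimum of 24h prior". This is not reconciled with item 7.
- The primary endpoint is "Analgesic requirements, rendered as opiate equivalents, at 12, 24 and 48 hours, and the 24 hours preceding both 72 and 96 hours postoperatively" (Section E).
- A note to Section E says the listed outcome data are captured in the electronic record for every patient, whether or not enrolled.
- The PI makes the final eligibility decision (Recruitment Method). No blinding to the postoperative course is stated.
- Matching of historical controls "will be blinded to outcomes" (Section D(3)). No similar statement covers entry to the BESB arm.
- Adverse events are tracked for enrolled patients (Section I).

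Section K defines no analysis set and no sensitivity analysis for patients who enter through item 7.

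**The concern.** In an open-label comparison with historical controls, the treated group should be fixed before its outcomes can be seen. The protocol applies that principle to the choice of controls but not to this route into the BESB arm. A patient whose first day went well may be more likely to be approached, and a family whose child had a poor course may be more likely to decline. The second mechanism needs no intent on the team's part.

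If good courses are favoured, mean opioid use in the BESB arm falls with no counterpart in the controls, and the error favours BESB. Safety is affected too. A clinical BESB patient with a complication who is never enrolled falls outside the adverse-event tracking, while uncomplicated late entrants enlarge the denominator. If such patients are not logged, neither effect can be assessed afterwards.

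**Working it through.** **Timing.** The block follows surgery, so it is placed close to time zero of the postoperative clock. A family first approached after the block and given at least a day consents at about 24 h or later. The 12-h value is then complete and the 24-h value probably so. With no deadline in item 7, later values could be known as well.

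**The plan's own sample size (Section L, Table 1).** Inputs: difference 0.18, SD 0.32, two-sided alpha 0.05, power 80%, ratio 1:2.

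BESB n = (1 + 1/2) × (1.960 + 0.842)² × 0.32² / 0.18² = 37.2, rounded up to 38, with 76 controls. The noncentral-t calculation also gives 38 and 76, with power 80.1%. The stated figure reproduces.

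**Size of a possible bias.** Inputs from the documents: 45 BESB patients and 90 controls; square-root 96-h OME with ERAS mean 1.231; SD 0.32 (BESB pilot group, used for sizing) or 0.211 (ERAS group), from Table 2. Assumptions not in the documents: m late entrants, all drawn from the lowest fraction f of a normal distribution, and no true effect.

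Spurious reduction = c × SD × m/45, where c = φ(z_f)/f:

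- f = 0.50: c = 0.399/0.50 = 0.798
- f = 0.75: c = 0.318/0.75 = 0.424

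With SD 0.32:

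| Late entrants of 45 | Lowest 50% | Lowest 75% |
|---|---|---|
| 2 | 0.011 (0.9%) | 0.006 (0.5%) |
| 5 | 0.028 (2.3%) | 0.015 (1.2%) |
| 8 | 0.045 (3.7%) | 0.024 (2.0%) |
| 10 | 0.057 (4.6%) | 0.030 (2.4%) |
| 15 | 0.085 (6.9%) | 0.045 (3.7%) |

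Percentages are relative to 1.231. Worked example: 0.798 × 0.32 × 5/45 = 0.028, which is 16% of the 0.18 target (0.028/0.18). With the ERAS SD the same case gives 0.798 × 0.211 × 5/45 = 0.019, about 10% of the target.

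**False-positive rate favouring BESB.** This was simulated with 20,000 trials per scenario, 45 versus 90 patients, SD 0.32, no true effect and a two-sided 0.05 t-test. The nominal rate in this direction is 2.5%. Each range runs from lowest-75% to lowest-50% selection:

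- 2 late entrants: 3.4% to 3.9%
- 5: 4.2% to 6.7%
- 10: 6.9% to 15.0%
- 15: 11.3% to 30.4%

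**Room in the sample size.** 45 − 38 = 7. The end of Section L already assigns that margin to withdrawals, procedural changes and intraoperative exclusions.

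**The case against.** The strongest reply is that the route is narrow and its timing is not stated. Item 7 is called exceptional, entry criteria must be met, and its named trigger, a schedule change, has nothing to do with outcome. The Recruitment Method also says that all families scheduled for an eligible procedure will be contacted, and that BESBs are not usual for this surgery at the hospital, which suggests a small pool. Section D(3) has a research-team member supervising placement and the activity monitor fitted on the day of surgery, which fits contact before the block better than after it.

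Much of this stands. A reader might infer that the protocol openly permits enrolment once outcomes are known, or that the BESB arm will in fact be selected on outcome. The documents do not support either statement: post-block approach is the natural reading but remains an inference, and nothing shows that selection will occur.

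Three limits on size also stand:

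- Lower-half selection is a strong assumption. Late entrants chosen on 12-h or 24-h values would be less strongly selected on the 96-h total.
- On untransformed OME, 5 late entrants give 0.798 × 0.724 × 5/45 / 1.557 = 4.1%. The trial is sized on the square-root scale, where the figure is 2.3%.
- Ten of 45 is hard to square with an exceptional route.

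The reply does not remove the point. The second trigger is undefined, and the contact-all rule is written for scheduled patients and may not bind item 7. Section B says that staff and families at the hospital frequently request these blocks, so the number of late entrants is unknown rather than known to be small.

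**Conclusion.** The point holds as a gap in the plan. Item 7, on its natural reading, opens a route into the BESB arm that can depend on outcome, and no safeguard covers it. Its size cannot be derived from the documents. Over the assumptions shown, the spurious reduction is 0.006 to 0.011 for 2 late entrants and 0.015 to 0.028 for 5, against a target of 0.18. That is small if few patients enter this way, and it becomes material at about 10 or more of 45. It comes on top of the limits already accepted with an open-label, historically controlled design.

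A reader might also infer that late entrants can be dropped at no cost because 45 exceeds 38 by 7. They cannot, since that margin is already committed. The change is nevertheless worth making: it is cheap, and without a log the bias could not be assessed later.

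**What to change.** State in item 7 whether a family may be approached after block placement. If not, one sentence closes the point. If so:

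- log every eligible patient who receives a clinical BESB, including those not approached and those who decline;
- approach all of them consecutively;
- record consent time relative to block placement;
- define the primary analysis set as patients consented before placement, and add late entrants only in a labelled sensitivity analysis.

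The cost is a log, a short amendment to item 7 and Section K, and possibly a few fewer patients in the primary set. Late entrants should not count toward the 45. Otherwise, power should be restated for the number remaining: for a difference of 0.18 and SD 0.32 it is 86.4% with 45 and 90 patients, and 80.1% with 38 and 76. A flag with a sensitivity analysis excluding late entrants would be a lighter alternative, but it would leave the primary result exposed.

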### **(3) Description of Study Treatments or Exposures/Predictors**

Participants will have their medical record reviewed following enrollment for demographic information including: gender, age, weight and height, procedure, surgeon, and current and historical medication use.

Any other routine standard-of-care data will be collected preoperatively as well in addition to research-specific data points.

All enrolled patients will have bilateral erector spinae blocks (with catheters for postoperative local anesthetic infusion) placed by the by a member of the BCH regional anesthesia team (under the supervision of a member of the research team) in a sterile fashion after the cardiac surgical procedure is completed. The placement is as follows:

- The patient is placed in a lateral decubitus position (left or right), with all pressure points padded in routine fashion.
- The area for intervention is prepped with a chlorhexidine solution, and sterile drapes are applied to demarcate the block placement area.
- The T4/5 transverse process on one side is identified with the ultrasound transducer in a parasagittal orientation.
- An 18g Tuohy needle is advanced to the target area under direct ultrasound visualization. The needle tip is advanced until it contacts the transverse process, just below the erector spinae muscle complex.
- Normal saline is injected to confirm appropriate needle tip position. The erector spinae muscle is visualized to be elevated up off of the transverse process with normal saline injection
- With confirmation of appropriate needle tip position, the initial local anesthetic bolus is injected using a standard, weight-based dosing protocol.

- Following the bolus injection, a catheter is threaded into the space occupied by the local anesthetic bolus.
- Catheter tip position is verified by one or more of the following: ultrasound visualization of the catheter tip, ultrasound visualization of instilled normal saline and/or ultrasound visualization of a small hyperechoic (i.e. bright on ultrasound) injection of air.
- With the catheter tip position identified, the catheter is tunneled to a cutaneous exit point approximately 2-3cm from the incision using a Crawford needle.
- The catheter is dressed in standard fashion with an adhesive catheter anchor, Dermabond, Mastisol, Tegaderm and tape.
- This is repeated for the contralateral side. To the extent possible, this will be done without repositioning in a contralateral decubitus position.
- A label indicating that each catheter is a nerve-block catheter with its laterality and date of placement noted is applied to each catheter.
- Catheter placement is complete.
- Postoperative infusion of local anesthetic (ropivacaine) via the nerve block catheter is initiated and managed by the Acute Pain Service (per standardized, clinical weight-based protocols).
- Procedural notes:
  - Minor deviations from the above procedure (e.g. small changes in sequence, needle entrance locations, amount of catheter deployed, etc.) are possible as the anatomy, positioning, etc. of individual patients varies. This is anticipated and allowable so long as such modifications remain within what is currently considered standard of care for the placement of these blocks and what is done in a given case is considered the appropriate standard of clinical care for that patient by the clinical providers placing the block(s).

All patients will have access to the multimodal pain regimen which is standard of care for all ERAS Cardiac patient and includes acetaminophen and ketorolac, when otherwise not contraindicated, as well as pain-score based opiate rescue medications as needed. All patients have access to postoperative pain management as needed by means of a standard opioid-based PCA/NCA demand protocols utilized at BCH if needed. In addition, all enrolled patients will be followed by the Acute Pain Service at BCH as is the standard of care for all patients receiving nerve blocks, enabling access to additional assessment, catheter and infusion management (where appropriate) and opioid treatment as needed 24 hours a day, 7 days a week. In addition, one of the primary investigators will be available to the

Acute Pain Service staff for consultation 24 hours a day regarding any desired consultation on study patients.

Possible risks related to the block include bleeding, infection, local anesthetic systemic toxicity, local anesthetic insensitivity and incomplete block and/or block failure. These risks occur at no greater (or lesser) frequency than when associated with the use of such blocks in routine clinical situations.

Intraoperative and postoperative anesthetic and surgical data, routinely collected for the Society of Thoracic Surgery (STS), will be collected from the EMR.

In addition to observational tools and subjective scoring, patient functional status (activity, sleep quality and other measures) will be assessed by actigraphic analysis using the Fitbit™ Charge 3 smartwatch. A Fitbit™ will be placed on the non-dominant arm, if possible, after extubation on the day of surgery. The Fitbit™ will remain on the patient until discharge from the hospital (which on average is about 5 days post-op) and the actigraphic data subsequently will be downloaded to the secure research database and the data wiped from the device. If a study subject had an unforeseeable complication and they no longer progressed along the standard recovery path (e.g. re-intubation, return to ICU), or if the watch was interfering in clinical care in any way, the Fitbit™ would be removed.

Following primary data collection for the enrolled subjects, each subject will be matched by surgical procedure using the STS procedure code, to 2 patients within the cardiac surgery ERAS program QI database (IRB #P00029161 which allows retrospective data analysis of outcomes) by the research team. All patients recruited for this study are themselves already part of the enhanced recovery after cardiac surgery clinical program [QIP]. Matching will be performed 1:2 with respect to surgical procedure and diagnosis using the STS codes, within 30% of the study patient's age and according to gender (if possible) and will be blinded to outcomes. Thus, up to 90 additional patients will be included in this study, retrospectively in addition to the 45 study patients from the single arm interventional cohort study (BESB).

Groups will be compared for demographic data, risk factors (from the STS database), diagnosis, procedure and cardiopulmonary bypass and clamp times to ensure their similarities

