#### Specific Aims:

1. Evaluate the utility of BESB in cardiac surgical patients by assessing the pain scores, opioid consumption, and complications related to BESB.
2. Compare intra- and postoperative opioid use in patients receiving BESB vs. matched historical controls who did not receive BESB in the ERAS program.
3. Compare clinical outcomes between the 2 groups: duration of mechanical ventilation, time to mobilization, pain scores (median pain score per period), intensive care unit length of stay (LOS), incidence of postoperative nausea and vomiting, postoperative complications, hospital LOS, readmissions, mortality, recovery to baseline activity and sleep post discharge, total and rescue opioid pain medication requirements.
4. Evaluate quality of sleep and activity with (Fitbit™) smart watch device of patients receiving BESB during the postoperative period.

**Hypothesis:** The investigators hypothesize that BESB is efficacious with respect to pain control and will lead to a 15% or greater reduction of consumed opiate equivalents at 12, 24 and 48 hours, and the 24-hour period preceding both 72 and

96 hours postoperatively compared to matched historical controls who received standard of care pain management (systemic opioid therapy).

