## **D. Design and Methods**

### **(1) Study Design**

We propose a single arm, open label, interventional study to compare the opiate requirements of 45 patients who consent to receive BESB catheters following cardiac surgery via sternotomy versus 90 matched historical controls who had similar surgical procedures but without BESBs.

Patients meeting eligibility criteria will be recruited and enrolled to have BESBs placed for postoperative pain control as a part of their perioperative anesthetic

plan. These patients will subsequently have a variety of preoperative demographic and functional data collected as well as data related to their surgeries and postoperative course all collected for later analysis. This enrolled group of patients will subsequently be compared regarding these outcome measures with a 1:2 matched, retrospective analysis of patients in the cardiac surgical ERAS program who did not receive regional blocks as a component of their anesthetic care. (The ERAS Cardiac program is a heart center perioperative evidence-based quality initiative. Retrospective data analysis of outcomes for patients in this program is performed for quality improvement purposes and outcomes research [IRB P00029161 – PI: [name] MD, co-investigators: [name] MD, [name] MD]). Children aged 2 years through 17 years meeting entry criteria will be screened and recruited for participation from the Boston Children's Hospital cardiac surgical program.

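### Date of surgery is in neither the control matching, the comparability check nor the analysis, so any change over time in ERAS opioid practice is confounded with BESB.

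*Combined protocol and SAP*

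**What the plan says.** Section A (Specific Aims) sets the comparison against "matched historical controls who did not receive BESB in the ERAS program". Section D(1) describes the source of those controls: "The ERAS Cardiac program is a heart center perioperative evidence-based quality initiative".

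Section D(3) gives the matching rule. It runs after the BESB data are in: "Following primary data collection for the enrolled subjects, each subject will be matched by surgical procedure using the STS procedure code". The factors are stated as "Matching will be performed 1:2 with respect to surgical procedure and diagnosis using the STS codes", then "within 30% of the study patient's age and according to gender (if possible) and will be blinded to outcomes". No date range or calendar window is given for the controls. The same section lists the comparability checks: "Groups will be compared for demographic data, risk factors (from the STS database), diagnosis, procedure and cardiopulmonary bypass and clamp times". Date of surgery is not in that list.

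Section K plans t-tests, or Wilcoxon rank-sum tests if the data are not normal, with no covariates. Recruitment of the BESB arm is expected to take about 2 years (sections D(2) and H).

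On intraoperative opioid, Aim 2 is to "Compare intra- and postoperative opioid use in patients receiving BESB", whereas section D(3) has the blocks placed "in a sterile fashion after the cardiac surgical procedure is completed".

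**The concern.** With historical controls, treatment group and calendar time tend to move together. Time can be dealt with when controls are chosen, when the groups are checked for balance, or in the analysis. This plan does so at none of the three. The rule allows the oldest eligible record to be used even when a recent one would match equally well, and the planned tables would not show the reader that this had happened.

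The controls come from a quality initiative, so it is reasonable to ask whether practice changed within it. If non-block opioid use differs between the two periods, the difference passes one-for-one into the primary comparison. More patients do not help, because this is bias: a larger sample makes a spurious difference more likely to reach significance.

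Aim 2 raises a smaller, related point. Opioid given before the block is placed cannot be an effect of the block, yet the aim lists intraoperative use among the BESB comparisons.

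**Working it through.** **Inputs.** From section L, Table 1: control mean 1.23 for square-root 96-hour OME, SD 0.32, difference 0.18, two-sided 5% level, 38 BESB and 76 controls. From Table 2: ERAS pilot SD 0.211. Planned enrolment is 45 and 90. The size of any drift is not in the documents and is assumed below.

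**Reproducing the plan's figure.** SE = 0.32 × √(1/38 + 1/76) = 0.0636. Then 0.18/0.0636 = 2.83, and the noncentral-t power is 80%, as stated. For the 48-hour outcome (difference 0.16, SD 0.26) the normal approximation gives 87%, also as stated. The sample size calculation is not in question.

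**Smallest significant difference.** 1.96 × 0.0636 = 0.125 at 38/76, which is 10% of 1.23. At 45/90, SE = 0.32 × √(1/45 + 1/90) = 0.0584, so 1.96 × 0.0584 = 0.115, or 9% of 1.23.

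**Drift with no block effect.** If untreated raw OME is lower by a proportion f in the BESB period, the square-root mean is multiplied by √(1 − f). The spurious difference is d = 1.23 × (1 − √(1 − f)). For f = 10%, √0.9 = 0.949, so d = 1.23 × 0.0513 = 0.063 and d/SE = 0.063/0.0636 = 0.99. The probability of a significant result at each f, from the noncentral t with SD 0.32, is:

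| Assumed raw fall | Fall on square-root scale | d | 38/76 | 45/90 |
|---|---|---|---|---|
| 0% | 0% | 0 | 5% | 5% |
| 5% | 2.5% | 0.031 | 7.7% | 8.3% |
| 10% | 5.1% | 0.063 | 17% | 19% |
| 15% | 7.8% | 0.096 | 32% | 37% |
| 20% | 10.6% | 0.130 | 53% | 60% |

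With the smaller ERAS pilot SD (0.211) in both groups, a 10% fall gives 32% and 37%.

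**The opposite direction.** If raw OME were instead 10% higher in the BESB period, the shift is 1.23 × (√1.1 − 1) = 0.060. A true difference of 0.18 would then appear as 0.12. Power would drop from 80% to about 46% at 38/76, and from 86% to about 53% at 45/90.

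**From annual rates to a total.** The raw fall over y years at annual rate r is 1 − (1 − r)^y. For r = 2%, 5% and 10% and y = 2, this is 4%, 10% and 19% raw, or 2%, 5% and 10% on the square-root scale. Both r and y are assumptions.

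**Price of adjustment.** If date explains a share R² of the variance in group membership, the effective SD is 0.32/√(1 − R²). At 45/90 and a difference of 0.18, power is about 75% for R² = 25% (SD 0.370) and 58% for R² = 50% (SD 0.453). These R² values are also assumed.

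**The case against.** The strongest reply is that drift is nowhere shown. A reader might infer that the comparison is biased towards BESB, because section B links the growth of regional anesthesia to concern about opioid harm. That passage is about the field; it does not describe non-block opioid dosing in this ERAS programme. Use there may have been stable or rising. This reply stands, and the direction has to be left open.

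Second, the plan has safeguards. Controls come from the same programme, with the same multimodal regimen and opioid rescue driven by pain scores, and matching is blinded to outcomes. These deal with programme entry and with picking records for their opioid use. They do not deal with change inside the programme. Section B also concedes that a randomised trial would be ideal, but does not mention time trend.

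Third, a reader might set a raw drift of 10% or 19% directly against the 15% threshold. Section A can be read on the raw scale, but section L powers 15% on square-root OME. On that scale those drifts are about 5% and 10%, and 15% corresponds to a raw fall of about 28% (1 − 0.85²). So none of the annual-rate scenarios reaches 15% there, although each inflates the error rate.

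Fourth, a reader might treat an intraoperative opioid difference as proof of drift. The documents do not allow that. In an open-label study the anesthesia team may dose in anticipation of the block, and some dosing may follow the bolus but precede OR exit.

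**Conclusion.** The concern holds as a conditional one. Date of surgery is uncontrolled in selection, balance check and analysis, so any time trend in ERAS opioid use is inseparable from the BESB effect. A fall would favour BESB and a rise would conceal a benefit. How large the trend is, and which way it runs, cannot be learned from the documents.

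Under assumed falls of 10% and 20% in raw 96-hour OME and no block effect, the two-sided error rate rises from 5% to about 17% and 53% at 38/76, and to about 19% and 60% at 45/90. These figures assume a proportional shift, SD 0.32 in both groups and a t-test on the square-root scale. If some controls turn out to be concurrent, which the plan neither requires nor excludes, the bias would be smaller.

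The change should be made before matching begins. The section between L and N was not in the text available for this check.

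**What to change.** 1. **Selection.** Among patients who meet the current matching rules, take the two nearest in date of surgery, still blinded to outcomes. If concurrent non-block patients are eligible, apply the study's exclusion criteria to them and report how many controls are concurrent.
2. **Reporting.** State the control date range, add date of surgery by group to the comparability table, and show control OME by date.
3. **Sensitivity analysis.** Repeat the primary comparison adjusted for date. Label it as less precise, and as extrapolation if the two periods do not overlap.
4. **Intraoperative opioid.** Report opioid given before block placement as a descriptive comparability check that may reflect practice change or open-label anticipation. Do not interpret it as a BESB effect.

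The cost is one extra selection criterion, a few table rows and one further analysis, with no additional patients. Gender matches may be slightly fewer, and the adjusted analysis loses power as calculated above. Nearest-date selection can narrow the gap only as far as the available pool allows, and the plan does not give the size of that pool.
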